18.0 Analytical Plan

All statistical analysis will be performed using SAS® version 9.3 or later, unless otherwise stated. All statistical tests will be two-sided and interpreted at a 5% significance level.

Descriptive statistics (i.e., mean, standard deviation, median, minimum, maximum, etc.) will be provided for all continuous variables; frequencies and percentages will be tabulated for incidence and categorical variables. For parameters measured over time, observed values and changes from baseline will be described for each time point.

The Mycologically Proven Recurrence and Mycological Eradication rates will be described by baseline *Candida* species, when the number of isolates per species allows.

The percentage of subjects with Mycologically Proven Recurrence will be described by number of VVC episodes in the 12 months prior to randomization.

All analyses will be presented by treatment group, as appropriate. Unless otherwise stated, data will be analyzed as is with no imputation. No adjustment for multiplicity will be employed.

A Statistical Analysis Plan (SAP) describing all final statistical analyses in detail will be provided as a separate document. The SAP will be finalized prior to the unblinding of the study treatments for analysis.

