18.1 Sample Size Determination

The primary endpoint of the study is the percentage of subjects with documented Clinical Success up to TOC (Week 24). Assuming response rates of 65% and 43% for ibrexafungerp and placebo, respectively; 90% power; and an alpha level of 0.05, approximately 240 subjects randomized at a 1:1 ratio are needed to declare a difference between ibrexafungerp and placebo at Week 24 based on Fisher's Exact test.

In order to be randomized, a subject should have achieved the proposed significant resolution of signs and symptoms (total composite score ≤ 2 on the VSS Scale) after receiving fluconazole therapy for an acute episode and have a positive culture for *Candida* spp. from the sample collected at Screening. It is estimated that approximately 320 subjects will need to enter the Acute Phase to provide 240 subjects randomized to the Prevention of Recurrence Phase. Enrollment into the Acute Phase will be discontinued when approximately 240 subjects have been randomized.

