18.2 Analysis Populations

The study populations to be used in the analyses are defined as follows:

- **Intent-to-Treat (ITT) Population:** All randomized subjects.

- **Modified Intent-to-Treat (mITT) Population:** All randomized subjects who have a confirmed mycological culture for yeast at Screening and a negative culture for yeast at Baseline (Day 1).
- **Per-Protocol (PP) Population:** All ITT subjects who did not have major protocol deviations likely to affect study efficacy and who have available data at the TOC visit. Note that subjects who discontinue due to a study-drug-related AE will be classified as failures for the analyses of efficacy under the PP population.
- **Safety Population:** All randomized subjects who received at least one dose of study drug (ibrexafungerp or placebo) and who have at least one post-Baseline (Day 1) evaluation.

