18.3 Subject Disposition, Discontinuation, and Baseline Data

Subject disposition in terms of the number and percentage of subjects enrolled by site will be tabulated. The number of subjects randomized, number completing the study, and reasons for discontinuation will be summarized by treatment group. Subject demographics and baseline characteristics such as age, race, ethnicity, sex, weight, height, body mass index, region (if applicable) and other relevant parameters will be tabulated by treatment group.

Baseline is defined as the last non-missing assessment prior to the date (and time if appropriate) of the first dose of study drug. Change from baseline is defined as: post-baseline value – baseline value.

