18.4 Handling of Missing Data, Dose Adjustments, and Early Withdrawals

For the efficacy analyses, subjects who do not have a TOC (Week 24) assessment will be assigned as treatment failures. For subjects who withdraw from the study early, every effort will be made to collect TOC or EOFU visit information (as applicable) at the point of withdrawal. Missing data will be further described in the SAP for early withdrawal subjects.

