#### **4.3. Analysis Set**

Intent-to-Treat (ITT) Set: All randomized subjects who received at least one dose of study drug (ibrexafungerp or placebo).

Modified Intent-to-Treat (mITT) Set: All randomized subjects who received at least one dose of study drug (ibrexafungerp or placebo), who have a confirmed mycological culture for yeast at Screening and a negative culture for yeast at Baseline (Day 1).

Per-Protocol (PP) Set: All mITT subjects who did not have major protocol deviations likely to affect study efficacy and who have available data at the TOC visit. Note that subjects who discontinue due to a study-drug-related AE will be classified as failures for the analyses of efficacy under the PP population.

Safety Set (SS): All randomized subjects who received at least one dose of study drug (ibrexafungerp or placebo) and who have at least one post-baseline evaluation.

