#### **4.4. Handing of missing data**

##### **4.4.1. Non-Responder Imputation (NRI) for Categorical Responses**

For clinical responses which described in section 8.1, and 8.2.1, a subject who has not previously experienced a failure response of the endpoint of interest and does not have the required assessment of potential recurrence data at Week 4 (or Week 8, Week 12, Week 24 (TOC) and Week 36 (EOFU)) for any reason will be considered as failure in the analysis of the specified time point. If one or more of the required assessments of potential recurrence are not completed within Week 4 (or Week 8, Week 12, Week 24 (TOC) and Week 36 (EOFU)), the subject will be considered as failure. Randomized and took at least 1 study treatment patients without at least 1 post-baseline observation will also be defined as failure for the NRI analysis.

For mycological outcome, subjects will be considered a non-responder for the NRI analysis if their mycological outcome cannot be determined due to early termination before the specified visit or missing mycological data at the specific visit. Randomized subjects without at least 1 post-baseline observation will also be defined as non-responder for the NRI analysis.

Randomized subjects without study treatment will be excluded from all analysis.

The NRI may be applied at any time point specified for analysis.

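### The SAP's primary set, still named ITT, omits women randomised but never dosed, so no planned efficacy analysis covers everyone randomised

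*SAP*

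**What the plan says.** Protocol 18.2 defines the ITT population as "All randomized subjects", and 18.6.2 names it the primary analysis population. For efficacy, Protocol 18.4 says that "subjects who do not have a TOC (Week 24) assessment will be assigned as treatment failures", and 18.6.2 repeats this for the primary endpoint.

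SAP 4.3 uses the same label for a narrower set: "All randomized subjects who received at least one dose of study drug (ibrexafungerp or placebo"). SAP 8 and 8.1.1 make that set primary. SAP 4.4.1, on non-responder imputation (NRI), then states: "Randomized subjects without study treatment will be excluded from all analysis". SAP 11 lists the new ITT and mITT definitions among its changes from the protocol, without a reason. Its wording adds a signed consent form as a condition, which SAP 4.3 does not have, so the SAP words its own primary set in two ways.

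On disposition, Protocol 18.3 says: "The number of subjects randomized, number completing the study, and reasons for discontinuation will be summarized by treatment group". The SAP 5.1 table is presented for the ITT and mITT sets, with percentages based on those sets.

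**The concern.** Randomisation supports a comparison of everyone randomised. A woman who is randomised, is never dosed and has no TOC evaluation counts as a failure under the protocol. Under the SAP she is in neither numerator nor denominator, yet the result would be reported as ITT.

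No other planned analysis recovers her. The SAP's mITT set also requires a dose, its per-protocol set is drawn from mITT, and its safety set requires a dose. The sensitivity analysis in SAP 8.1.1 goes the other way and removes women whose outcome was imputed.

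SAP 4.4.1 is also inconsistent within itself. For mycological outcome it makes randomised subjects with no post-baseline observation non-responders, with no dosing condition. Its next paragraph excludes the undosed. An undosed woman with no post-baseline data meets both rules.

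**Working it through.** **The plan's own figure.** Inputs from Protocol 18.1: "Assuming response rates of 65% and 43% for ibrexafungerp and placebo, respectively; 90% power; and an alpha level of 0.05", and "approximately 240 subjects randomized at a 1:1 ratio are needed to declare a difference between ibrexafungerp and placebo at Week 24", using Fisher's exact test. Protocol 18.0 adds: "All statistical tests will be two-sided and interpreted at a 5% significance level". Enumerating both binomial distributions at 120 per arm gives an exact two-sided Fisher power of 0.909, so the planned 240 is consistent with 90% power. The point does not depend on this figure, which only supplies rates for gauging size.

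**Assumptions.** The documents do not say how many women will be randomised but not dosed, so the number *u* in an arm of 120 is assumed. Success is taken as 65% and 43% among dosed women, and every undosed woman is taken to fail.

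**Formulae.** SAP rule: rate = *p*, since undosed women leave the denominator. Protocol rule: rate = *p* × (120 − *u*)/120.

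| Undosed: ibrexafungerp, placebo | Protocol-rule rates | Protocol-rule difference (points) | SAP difference (points) |
|---|---|---|---|
| 0, 0 | 65.0% v 43.0% | 22.0 | 22.0 |
| 2% of each arm | 63.7% v 42.1% | 21.6 | 22.0 |
| 5, 5 | 62.3% v 41.2% | 21.1 | 22.0 |
| 5, 0 | 62.3% v 43.0% | 19.3 | 22.0 |
| 0, 5 | 65.0% v 41.2% | 23.8 | 22.0 |

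Steps:
- 2% of each arm: 0.65 × 0.98 = 0.637 and 0.43 × 0.98 = 0.4214; the difference is 0.2156.
- One arm only: 2% of 240 is 4.8 women, taken as 5. If all are on ibrexafungerp, 0.65 × 115/120 = 0.623 and 0.623 − 0.43 = 0.193. If all are on placebo, 0.43 × 115/120 = 0.412 and 0.65 − 0.412 = 0.238.

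The one-sided shifts are therefore 22.0 − 19.3 = 2.7 points and 23.8 − 22.0 = 1.8 points, in opposite directions.

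**Power, exact Fisher.** With 2 undosed per arm, power is 0.897 under the protocol rule and 0.909 with exclusion. With 5 per arm, it is 0.879 and 0.908.

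**The case against.** The strongest reply is that the change is declared, in a SAP that Protocol 18.0 requires to be final before unblinding, and that it will touch almost nobody. Randomisation and the first on-site dose both fall on Day 1 (Protocol 14.15 and 14.16) and the trial is double-blind, so few undosed women and little imbalance between arms are expected. That stands, and it is why the point is minor. It does not supply the missing reason or make the ITT label accurate.

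Four stronger readings are tempting, and the documents do not support them.

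- *The SAP drops the rule that missing means failure.* It does so only for undosed women. Dosed women with missing or incomplete assessments are still failures under SAP 4.4.1 and 8.1.1.
- *Every undosed woman is a certain failure under the protocol.* She is one only if she has no TOC evaluation. Protocol 11.3 asks for the TOC procedures at early discontinuation and does not say whether these count as a TOC evaluation. The explicit rule that early termination before TOC is failure is in SAP 8.1.
- *The exclusion always flatters the drug.* It does if undosed numbers are balanced or fall on ibrexafungerp. If they fall on placebo, it understates the difference.
- *The number randomised cannot be recovered.* SAP 5.1 also plans a flowchart of women entering the prevention phase, where randomisation occurs, with the analysis-set counts, and a disposition listing; SAP 4 sorts listings by treatment group. What remains is narrower: neither the table nor the flowchart promises randomised and undosed counts by arm.

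It is also fair to object that restoring the full set takes more than a change of wording. Baseline, study day and time to first recurrence are all anchored to first dose (SAP 4 and 8.2.1), so they are undefined for an undosed woman.

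**Conclusion.** The point holds as a disclosed but unexplained narrowing of the primary population. It is not a hidden departure, and it is not evidence of bias in a known direction. The protocol's primary analysis covers all randomised women; the SAP's covers dosed women under the same name, with no efficacy analysis of the full set.

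The likely size is small: 0.4 points on the difference if 2% of each arm is undosed, and up to about 2.7 points, in either direction depending on the arm, if about five undosed women all fall in one arm. These sizes rest on assumed undosed counts, the planning rates applying among dosed women, and all undosed women failing. If nobody is undosed, nothing changes. The correction is worth making because it is cheap and keeps the primary comparison on everyone randomised.

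**What to change.** 1. In SAP 4.3, restore ITT as all randomised subjects, and use it as the primary set for the primary endpoint and the other categorical efficacy endpoints.
2. Score undosed women without a TOC evaluation as failures under the existing NRI rule.
3. Delete the exclusion sentence in SAP 4.4.1 and the ITT bullet in SAP 11. Align the mITT definition and its Section 11 bullet with Protocol 18.2. This also removes the two wordings of the primary set.
4. Use the randomisation date as time origin and baseline anchor for undosed women.
5. Keep the dosed set, under another name, as a supportive analysis. The safety set is unaffected, since the protocol already requires a dose for it.
6. In the disposition table, give the number randomised, and the number randomised but not dosed, by arm.

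The cost is some SAP rewording and a little extra programming for the date anchors and the disposition rows. Reported success rates may be slightly less favourable. If the sponsor prefers to keep the dosed set primary, the minimum is to rename it, give the reason, report the undosed count by arm and add an all-randomised sensitivity analysis of the primary endpoint.

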##### **4.4.2. Last Observation Carried Forward (LOCF)**

A LOCF analysis will be performed on health outcome variables, including EQ-5D Summary Index and EQ VAS, all 8 scale scores and 2 overall scores of SF-36, and FSDS total score. The last non-missing post-baseline observation will be carried forward to the corresponding endpoint for evaluation. For patients that take rescue therapy, their last non-missing observation up to the date of the rescue medication will be carried forward to the corresponding endpoint for evaluation. Randomized patients without at least 1 postbaseline observation will not be included for evaluation.

## **5. Subject Disposition**

### **5.1. Disposition**

A flowchart diagram includes the number of subjects who screened, subjects who screen failed before acute phase, subjects who entered acute phase, subjects who discontinued after acute phase,

subjects who entered the nested sub-study, subjects who entered the prevention of recurrence phase, will be presented.

For subjects who entered the nested sub-study, the following categories should be presented: subjects in each analysis set (ITT, mITT, SS), subjects who completed TOC visit, subjects who completed the study, subjects who discontinued from the study, and the reasons for study discontinuation.

For subjects who entered the prevention of recurrence phase, the following categories should be presented: subjects in each analysis set (ITT, mITT, PP, SS), subjects who completed TOC visit, subjects who completed the study, subjects who discontinued from the study, and the reasons for study discontinuation.

A disposition table of subjects includes the number and percentage of subjects for the following categories: subjects in each analysis set (ITT, mITT, PP, SS), subjects who completed TOC visit, subjects who completed the study, subjects who discontinued from the study, and the reasons for study discontinuation will be presented by the ITT and mITT sets. All percentages will be based on the number of subjects in each corresponding set.

The reason for study discontinuation may include any of the following: Absence of culture-confirmed *Candida* spp. infection from the sample reviewed at Baseline, Adverse Event, Lost to Follow-up, Physician Decision, Pregnancy, Study Terminated by Sponsor, Withdrawal by Parent or Guardian, Withdrawal by Subject, Other, Death, Trial Screen Failure.

Subject disposition data will be presented in a listing.

## **5.2. Protocol Deviations**

The investigator may not deviate from the protocol without a formal protocol amendment having been established and approved by an appropriate IRB, except when necessary to eliminate immediate hazards to the subject or when the change(s) involve(s) only logistical or administrative aspects of the study.

Significant protocol deviations will be defined in the significant protocol deviations rules document. Each significant deviation will be assigned a rule number. As the study is ongoing, additional significant protocol deviations can also be spontaneously identified or defined by the sponsor and/or the project team during the regularly planned study deviation review meetings and the significant protocol deviations rules document can be updated.

All protocol deviations will be reviewed and assessed as to significance and severity for the purposes of analysis prior to the database lock.

All major protocol deviations (i.e. resulting in exclusion of the subjects from one or more analysis) will be summarized using the ITT and mITT sets.

Major protocol deviations will also be presented in a listing.

## 6. Demographics and Baseline Characteristics

### 6.1. Demographics

A summary of the following demographics will be presented for the subjects in ITT set and mITT set, respectively.

- Age (years);
- Age group (<18 years, 18 -<36 years, 36 -<50 years, 50 -<65 years, ≥65 years);
- Sex (Female);
- Race (White, Black or African American, Asian, American Indian or Alaska Native, Native Hawaiian or Other Pacific Islander, and Other);
- Ethnicity (Hispanic or Latino, Not Hispanic or Latino);
- Country [USA (United States), BGR (Bulgaria), RUS (Russia), POL (Poland)];
- Geographical location (USA, EX-USA);
- BMI (kg/m^2);
- BMI group (Underweight <18.5 kg/m^2, Normal 18.5-<25 kg/m^2, Overweight 25-<30 kg/m^2, Obese 30-<40 kg/m^2 and Morbidly Obese ≥40 kg/m^2);
- BMI group (≤35 kg/m^2 and >35 kg/m^2).

The age collected in CRF will be used for analysis if it is non-missing. If the age is not collected in the CRF, the age in years is calculated using the date of the informed consent and date of birth.

$$\text{Age (years)} = [(\text{Informed Consent Date} - \text{Date of Birth} + 1) / 365.25].$$

BMI is calculated as

$$\text{BMI} = (\text{body weight in kilograms}) / (\text{height in meters})^2.$$

Demographics for all subjects in the ITT set will be presented in a listing.

### 6.2. Baseline Characteristics

A summary of the following baseline characteristics will be presented for subjects in the ITT and mITT sets, respectively.

- Number of recurrent VVC episodes in the prior year;
- Uncontrolled diabetes mellitus (Yes or No);
- Candida species at screening (by Genus species);
- Candida species at baseline (by Genus species);
- Composite score of the vulvovaginal signs and symptoms at screening;

- Severity of VVC at screening (the composite score of the vulvovaginal signs and symptoms at screening ‘4 - 7’, ‘8 - 12’, and ‘>=13’);
- Severity of VVC at screening (the composite score of the vulvovaginal signs and symptoms at screening <7, >=7);
- Total score of Female Sexual Distress Scale at baseline;
- Categorical responses of the 5 EQ-5D dimensions, EQ VAS score, and EQ-5D index score at baseline;
- SF-36 PCS and MCS;
- Fertility Status (Surgically Sterile/Infertile, Post-Menopausal, Potentially Able to Bear Children);
- Method of Birth Control (Barrier Methods Only, Oral Contraceptives, Depo Contraceptives (Implants/Injectables), IUD, Abstinence, Vaginal Ring, Vasectomized Partner, None, Other);

A separate summary table will be presented to include MIC range, mode, MIC50, and MIC90 by treatment group and geographical region (USA or Ex-USA) for the following MIC results from 2 different methods, CLSI and EUCAST, respectively:

- MIC results for SCY-078 and fluconazole (FLU) at 24 hours against candida species isolates obtained at Screening for all subjects in the ITT, mITT and PP sets;
- MIC results for SCY-078 and fluconazole (FLU) at 48 hours against candida species isolates obtained at Screening for all subjects in the ITT, mITT and PP sets.
- MIC results for SCY-078 and fluconazole (FLU) at 24 hours against candida species isolates obtained at Baseline for all subjects in the ITT set;
- MIC results for SCY-078 and fluconazole (FLU) at 48 hours against candida species isolates obtained at Baseline for all subjects in the ITT set.

Baseline characteristics for all subjects in ITT set will be presented in a listing.

### **6.3. Medical History**

Medical history will be coded according to the Medical Dictionary for Regulatory Activities (MedDRA; Version 19.1 or higher). A frequency summary (number and percentage) of subjects with at least one medical history will be presented by system organ class (SOC), and preferred term (PT), with SOCs sorted in alphabetical order and PTs within each SOC in descending order of frequency for all subjects in the ITT and mITT sets.

In addition, A summary of other vulvovaginal conditions (Selected SOC and PTs) will be presented by SOC, and PT for subjects in the mITT set.

A by-subject listing of medical history will be provided for all subjects in the ITT set.

## 6.4. Inclusion and Exclusion Criteria

Prior to both screening and randomization, the investigator will assess if the subject fulfills all of the inclusion and none of the exclusion criteria outlined in the protocol (sections 11.1 and 11.2). The specific inclusion criterion not met or exclusion criterion which was met will be recorded in the eCRF.

## 7. Treatments and Medications

### 7.1. Prior and Concomitant Medications

All prior and concomitant medications taken from 28 days before screening through the Week 24 (TOC) visit will be recorded. Only the use of other antifungal medications, medications used to treat vaginal bacterial or parasitic infections, topical vaginal medications or medications to treat a study-drug related AE will be recorded after the TOC visit through the last study visit (Week 36 (EOFU)).

A summary with the number and percentage of subjects who took medications will be presented by WHO therapeutic drug class and generic drug name for those subjects who discontinued before entering the prevention of recurrence phase or the nested sub-study. In addition, a by-subject listing of medications will be provided.

For the purpose of inclusion in prior and/or concomitant medication tables, incomplete medication start and stop dates will be imputed as follows:

Missing start dates (where UK, UKN and UNKN indicate unknown or missing day, month and year respectively):

- UK-MMM-YYYY: Assume 01-MMM-YYYY. If the month and year are the same as the first dose of study drug month and year, then assume the date of first dose of study drug;
- UK-UKN-YYYY: If the year is prior to the year of first dose of study drug, assume 01-JAN-YYYY of the collected year. If the year is the same as the first dose of study drug year, then assume the date of first dose of study drug;
- UK-UKN- UNKN: Assume date of first dose of study drug.

Missing stop dates for concomitant medications data will be handled as follows (where UK, UKN and UNKN indicate unknown or missing day, month and year respectively):

- UK-MMM-YYYY: Assume the last day of the month;
- UK-UKN-YYYY: Assume 31-DEC-YYYY;
- UK-UKN- UNKN: Assume ongoing and leave it missing.

All prior and concomitant medications will be coded using the current version of the World Health Organization Drug Dictionary Enhanced (WHO-DD) and summarized by treatment group based on the ITT and mITT sets.

